Random observations of CHG baths will be performed throughout the entire study period by a designated clinician to ensure that all nurses are bathing the infants using the same technique. Each study team member actively bathing study subjects will be audited a minimum of once every two months. These observations will be documented on the CHG Bath Audit Tool (Appendix K) and scores of 15/15 points are acceptable. Any score lower than 15 will require retraining on the bathing technique. Also to facilitate reliable assessment of skin lesions, a CHG Erythema Assessment Tool (Appendix L) will be available for nurses to follow during their assessments (maintained at each study patients' bedside) (Figure 1.).

The sponsor-investigator will also engage the services of a qualified independent monitor to ensure the protection of the rights of human subjects, the safety of all subjects involved in the investigation and the quality and integrity of the data resulting from the trial. The independent monitor will conduct a pre-monitoring set-up visit and a monitoring visit after every fifth patient has been recruited and on the study for 1 week.

Data Analysis. With the support of a faculty statistician from the BCH Center for Patient Safety and Quality Research, we will use descriptive statistics including mean, median, range, and frequencies to describe the study sample and the findings (skin findings and adverse events). We will characterize the study sample on demographic and clinical characteristics. Our primary outcome measures will be proportion of subjects that experience any adverse event, and the rate of adverse events per 100 patient-days of follow-up. Our inferential statistics will calculate 95% confidence intervals around these estimates.

Research Question 1:

Are twice weekly CHG baths safe for use in a sample of infants 36 weeks PMA or older, and less than 2 months of age (48 weeks PMA) with a CVC?

Data Analysis 1:

Descriptive statistics including mean, median, range and frequencies will be used to describe adverse events (including skin reactions and other untoward events). We will characterize the demographic and clinical characteristics of subjects that experience adverse events, although we will not perform hypothesis tests of association. We will consider time-to-rash data using Kaplan-Meier estimators.

Research Question 2:

Does twice weekly CHG baths lead to rising (cumulative) CHG blood levels, liver function tests (LFTs -AST/ALT) and Serum Creatinine over time in a sample of infants 36 weeks PMA or older, and less than 2 months of age (48 weeks PMA) with a CVC?

Data Analysis 2:

Descriptive statistics including mean, median, range and frequencies will be used to describe CHG, LFTs and serum Creatinine blood levels over time. We will examine scatterplots and other graphical analysis of blood level dispersion over time to look for relationships.

Sample Size Justification. The primary quantitative goal of this study is estimation of the adverse event rate per 100 patient days. The study sample size will impact the precision of this estimate, and we will establish an upper bound on the rate if zero adverse events occur. In this context, we designed the study sample to expand the existing knowledge base.

Based on recent safety data (Quach, et al 2014) on roughly 200 neonates which recorded no adverse events, we assume the rate of adverse events using CHG bath is lower than 5 events per 1000 days of post-exposure follow-up. We propose following N=50 subjects over 7 days of post-exposure follow-up, for a total of 350 observation days. Assuming rates of 3.5 events or 1.0 events per 1000 days of follow-up, the probability that at least one subject will experience an adverse event is roughly 83% or 40% respectively. Using Monte Carlo simulations, the mean upper bound for estimable rates is 5.5 events per 1000 days.

Auditing and Inspecting:

The sponsor-investigator will permit study-related monitoring, audits, and inspections by the Boston Children's Hospital IRB, the independent data monitor and government regulatory bodies, of all study related documents (e.g. source documents, regulatory documents, data collection instruments, study data etc.). The Investigator will ensure the capability for inspections of applicable study-related facilities.

Human Subjects:

BCH Committee for Clinical Investigation approval will be obtained before study procedures commence. All study staff will be Citi-program trained. Informed consent/HIPPA forms will be secured before initiation of any study procedures. A computerized database to track subjects through the research continuum will be developed and housed on a password-protected site behind the BCH firewall. Subjects will be assigned study ID numbers that will appear on all study materials and that will be utilized in place of subjects' names in the computerized database. A separate (electronic) CHG Study ID Assignment Log linking subject's names and ID numbers will be maintained by study personnel and kept in a locked cabinet behind a locked door. Only approved study personnel will have access to the log.

This study is considered greater than minimal risk with a potential for direct benefit. There is strong evidence that CHG will help prevent HAIs, however the safety profile for using CHG in infants less than 2 months of age (48 weeks PMA) is not known. To monitor for adverse events, the study team has developed a Data Safety Monitoring Plan (DSMP) and adverse event management plan (see Table 1). Adverse events to CHG baths include mild to severe skin lesions and possible absorption of CHG into the blood that could result in more serious problems such as respiratory, renal and liver problems or anaphylaxis. Thus the study team is taking a conservative approach. In an attempt to usurp the benefits associated with CHG while concurrently minimizing the likelihood of adverse events, study subjects will receive twice-weekly, instead of daily, CHG baths.

While these baths still place the subjects at risk for adverse events we believe twice-weekly baths will minimize these risks. To monitor for adverse events the study team has developed the following procedures:

1. Study RNs will perform a full body skin assessment for skin irritation or open areas prior to each bath.
2. Bedside RNs will complete skin assessments every 12 hours during the course of the study.
3. A plan is in place for Management of Adverse Events to the CHG Baths. (Table 1.)
4. To monitor for absorption into the blood, infants will have blood levels (CHG, ALT, AST, and Serum Creatinine) drawn at baseline and weekly and when an infant is removed from the study in response to an adverse event. In addition, infants will be monitored weekly for the development of iatrogenic anemia.

Data Safety Monitoring Plan:

The DSMC will review all adverse events experienced by the study subjects. All CHG levels obtained (up until the week prior to the meeting) will be available for review by the DSMC. The DSMC will consist of 5 expert clinicians throughout the institution including: a Clinical Nurse Specialist (skin care specialist), attending medical physician from the NICU or CICU, a Doctor of Pharmacy, an Infection Control expert and a Laboratory Medicine physician. They will assist the study team in making informed decisions about the management of adverse events, including study closure if warranted. At minimum, the PIs will contact members of the DSMC via email with a summary of the study findings, including available CHG levels, LFTs (AST/ALT), Serum Creatinine and HCT levels, at the following intervals during the course of the study:

- After the first 10 subjects have enrolled and participated in the study for a minimum of 2 weeks. During this meeting the DSMC will discuss the need to revise the plan (frequency) for obtaining LFTs, Serum Creatinine and HCT
- Following completion of the study by 25 subjects
- At the conclusion of the study

More frequent meetings may be required if serious adverse events are noted (Table 1, #5-8).

Adverse Event Management:

Criteria for Holding or Stopping the Study

Table 1 delineates criteria for holding and stopping rules for study subjects based on skin and lab and clinical assessments. Holding rules apply to study subjects that will no longer receive CHG baths, such as following the need for a blood transfusion, adverse event, or infants that become clinically unstable. Infants whose participation is placed on hold will have monitoring of daily vital signs (ranges), HCTs (if anemia was the cause of the hold), and documentation of significant clinical changes. This information will be recorded on the CHG Vital Sign and Clinical Monitoring Tool (Appendix M). Stopping rules apply to study participants that have had CHG baths placed on hold and have completed necessary monitoring described in holding rules. Furthermore, all adverse events will be recorded on the Adverse Event Reporting Tools.

Holding and Stopping Rules

Anemia/Blood Transfusions:

Holding rules for patients with anemia requiring blood transfusion. All study participants that require a blood transfusion while enrolled in the study will have CHG baths suspended until 1-week post transfusion and will have a pre- and post-transfusion assessment of vital signs (ranges-heart rate, respiratory rate, blood pressure, oxygenation requirement and means of respiratory support). A post-transfusion hematocrit will also be obtained, if not attained via standard of care, and documented on the CHG Blood Transfusion Tool (Appendix N). The CHG baths will resume 1-week post transfusion if study participant is deemed stable by both the study and medical teams.

Study participants that do not receive a blood transfusion or are deemed not stable will have monitoring of daily vital signs (ranges-heart rate, respiratory rate, blood pressure, oxygenation requirement and means of respiratory support), HCTs that are obtained as routine ICU care, and significant changes to clinical status for 1 month from cessation of CHG baths or until discharge, whichever comes first to assess for adverse events related to anemia.

Stopping rules for patients with anemia requiring blood transfusion. All study participants that have had CHG baths suspended and that do not receive a blood transfusion or are deemed unstable will be removed from the study after completing the clinical monitoring as described above.

Adverse Event (Other Than Anemia):

Holding rules for patients that experience an adverse event: All study participants that experience an adverse event, as described in table 1, and have CHG baths suspended due to the adverse event will have 2 CHG levels obtained within 1 week of CHG bath (recorded on CHG Lab Work Log), unless the previous level was not detectable. These infants will also have monitoring for adverse event symptom resolution and daily vital signs (ranges-heart rate, respiratory rate, blood pressure, oxygenation requirement and means of respiratory support) for 1 month from cessation of CHG baths or until discharge, whichever comes first.

Stopping rules for patients that experience an adverse event. All study participants that have CHG baths suspended due to an adverse event will be removed from the study after completing the clinical monitoring as described above.

Clinical Instability:

Holding rules for patients that become clinically unstable. For the safety of the study participant bathing will be suspended for infants demonstrating significant or acute impairment of their clinical status as indicated by their medical team. For example, patients requiring volume resuscitation due to blood and fluid losses, or a patient in the immediate post-operative period will not be bathed until return to baseline stability. These patients will have 2 CHG levels obtained within 1 week of last CHG bath, unless previous level was non-detectable. Infants deemed not appropriate for participation by either the study team or medical team will have monitoring of daily vital signs (ranges-heart rate, respiratory rate, blood pressure, oxygenation requirement and means of respiratory support) for 1 month from cessation of CHG baths or until discharge, whichever comes first.

Stopping rules for subjects that become clinically unstable. Study subjects whose clinical status does not return to baseline, as assessed by both the study and medical teams will be removed from the study after completing the clinical monitoring for 1 month as described above.

Table 1: Management of Adverse Events to CHG Baths

Erythema Assessment (see CHG Erythema Assessment Tool for visual comparisons)			
Finding	Action	Follow Holding and Stopping Rules	Reporting
1. Mild redness X1	None	Not Applicable	No immediate action; Send email update to PI; include in monthly DSMP report
2. Mild redness X2, persistent redness leading up to 2 nd bath, or moderate redness:	Discontinue CHG baths (unless rash is limited only to diaper area)	Adverse Event (Other Than Anemia)	Immediately reportable to PI; include in monthly DSMP report
3. Raised rash	Discontinue CHG baths (unless rash is limited only to diaper area)	Adverse Event (Other Than Anemia)	Immediately reportable to PI; include in monthly DSMP report
4. Blister(s)	Discontinue CHG baths	Adverse Event (Other Than Anemia)	Immediately reportable to PI; meet with DSMC
5. Open area(s)	Discontinue CHG baths	Adverse Event (Other Than Anemia)	Immediately reportable to PI; meet with DSMC

6. Evidence of systemic event	Discontinue CHG baths	Adverse Event (Other Than Anemia)	Immediately reportable to PI; meet with DSMC
7. Anaphylaxis	Discontinue CHG baths	Adverse Event (Other Than Anemia)	Immediately reportable to PI; meet with DSMC
Lab Value Assessment			
AST >70 u/l	Discontinue CHG baths	Adverse Event (Other Than Anemia)	Immediately reportable to PI; meet with DSMC
ALT >60 u/l	Discontinue CHG baths	Adverse Event (Other Than Anemia)	Immediately reportable to PI; meet with DSMC
Serum Creatinine 0.7 mg/dl or greater	Discontinue CHG baths	Adverse Event (Other Than Anemia)	Immediately reportable to PI; meet with DSMC
HCT <= 28%: Respiratory support (mechanical ventilation, continuous positive airway pressure or high flow nasal cannula with FiO ₂ > 25% Oxygen by nasal cannula > 1 liter/min) HCT <= 25%: No respiratory support	Discontinue CHG baths	Anemia/Blood Transfusions	Immediately reportable to PI; Discuss with medical team; meet with DSMC
Other			
Clinical Instability	Discontinue CHG baths	Clinical Instability	Immediately reportable to PI; include in monthly DSMP report

Financial Support:

This study is being funded by the Program for Patient Safety and Quality, the Department of Lab Medicine Clinical Chemistry Training Program, and the American Association of Critical Care Nurses. The nursing departments from the participating units will purchase the 2% CHG cloths for this study. The Department of Newborn Medicine will fund all supplemental laboratory specimens.

References:

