Untoward, Adverse Events Associated with CHG. While chlorhexidine has become a widely utilized antiseptic, it is not used without risk. With the assistance of [name] MLIS, the hospital librarian, an extensive literature search for untoward or adverse events associated with CHG revealed a number of concerning documents citing problems including mild skin irritation, Allergic Contact Dermatitis (ACD) and anaphylaxis. Most notably though, the more serious reactions were related from direct exposure to multiple products containing CHG and CHG impregnated devices (Khoo & Oziemski, 2010; Kutzscher, 2012), or direct contact between the CHG product and the mucous membranes of the individual. (Khan et al, 2011). In general, there were no serious events associated with CHG bathing cloths, with most reports citing only mild skin reactions. (Vernon et al, 2006; Bleasdale et al, 2007; Darmstadt et al, 2007; Sankar et al, 2009; Milstone et al, 2013).

Purpose Statement

Daily CHG baths are a proven method for preventing HAIs in patients greater than 2 months of age and older. However, CHG has been shown to be absorbed through the skin of premature and term infants and safe CHG bloodstream levels are not known. Thus the use of CHG in infants less than 2 months of age remains controversial.

Like many ICUs across the nation, the ICUs at Boston Children's Hospital have been using CHG on a limited basis for CVC insertion and CVC dressing changes on all babies greater than 28 weeks PMA for almost 2 years. During this time, we have not observed any untoward effects to the skin's surface. Though despite our best efforts, HAIs remain problematic, and thus we remain reluctant to expand the use to daily CHG baths without a better understanding of the risks and benefits. In effort to secure the benefit of CHG baths while minimizing risk of bloodstream absorption, our study team has elected to investigate the safety of twice-weekly 2% CHG baths in a sample of newborns (36 weeks PMA or older, less than 2 months of age or 48 weeks PMA, with a CVC). This study will examine the safety of twice weekly CHG baths and provide data to support a larger study that will examine efficacy. The research questions to be answered by this study are as follows:

Research Question 1:

Are twice weekly CHG baths safe for use in a sample of infants 36 weeks PMA or older, and less than 2 months of age (48 weeks PMA) with a CVC?

Hypothesis 1:

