CHG will be safe for use in a sample of infants 36 weeks PMA or older, and less than 2 months of age (48 weeks PMA) with a CVC as evidenced by an adverse event rate less than 10%.

Research Question 2:

Does twice weekly CHG baths lead to rising (cumulative) CHG blood levels, liver function tests (LFTs -AST/ALT) and Serum Creatinine over time in a sample of infants 36 weeks PMA or older, and less than 2 months of age (48 weeks PMA) with a CVC?

Hypothesis 2:

Twice weekly CHG baths do not lead to rising (cumulative) CHG blood levels, LFTs (AST/ALT)

and Serum Creatinine over time in a sample of infants 36 weeks PMA or older, and less than 2 months of age (48 weeks PMA) with a CVC.

Methods

Study Design: A pilot study using a single arm trial design.

Study Sample: Our convenience sample will include 50 infants. Infants admitted to the NICU or pediatric CICU will be eligible to participate.

Inclusion criteria.

- Greater than/equal to 36 weeks PMA (gestational age + chronological age)
- Less than/equal to 48 weeks PMA (gestational age + chronological age)
- Greater than/equal to 3 days of age
- Existing or soon to be placed, peripheral or surgical CVC
- Permission to participate in trial by attending physician
- Parent or legal guardian informed consent to participate in the trial

Exclusion criteria.

- Infant with a large open lesion or severe skin condition (i.e., Myelomeningocele, Gastroschisis, lymphatic malformation, open chest, ostomies and/or mucus fistulas or Icthyosis)
- Infants with active seizure disorders
- Infants with Hypoxic Ischemic Encephalopathy
- Infants with severe multi-system organ failure or Liver failure as defined by documentation of abnormal liver function tests: alanine aminotransferase (ALT) and aspartate aminotransferase (AST) Gamma-glutamyltransferase (GGT) and L-lactate dehydrogenase (LD).
- HCT \leq 28%: Respiratory support (mechanical ventilation, continuous positive airway pressure or high flow nasal cannula with FiO₂ > 25% Oxygen by nasal cannula > 1 liter/min) or HCT \leq 25%: No respiratory support.
- Infant with renal impairment as defined by: documented serum Creatinine greater than 0.7, renal disorders (renal agenesis, polycystic kidney disease, dysplastic kidneys, acute renal injury).
- Infants deemed clinically unstable by their physician such as patients that are extremely fragile and wouldn't tolerate the stimulation of the bathing process or those infants being considered for withdrawal of care.

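### Hypothesis 1 takes an adverse event rate below 10% as evidence of safety, but the plan does not tie that threshold to the planned 95% confidence interval or to N=50

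*Combined protocol and SAP*

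**What the plan says.** Four places in the combined protocol and SAP bear on this.

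- **Hypothesis 1 (Purpose Statement)** gives the criterion for safety: "as evidenced by an adverse event rate less than 10" percent. It gives no denominator and does not say whether the estimate or a confidence limit must be below 10%.
- **Data Analysis** names two primary measures: "proportion of subjects that experience any adverse event, and the rate of adverse events per 100 patient-days of follow-up". It adds: "Our inferential statistics will calculate 95% confidence intervals around these estimates". No interval method is named. Data Analysis 1, which serves Research Question 1, is descriptive with Kaplan-Meier estimates of time to rash and does not return to the 10%.
- **Sample Size Justification** says: "The primary quantitative goal of this study is estimation of the adverse event rate per 100 patient days". It promises that "we will establish an upper bound on the rate if zero adverse events occur", assumes a low rate ("we assume the rate of adverse events using CHG bath is lower than 5 events per 1000 days of post-exposure follow-up") and sets the size: "We propose following N=50 subjects over 7 days of post-exposure follow-up, for a total of 350 observation days". The 10% does not appear.
- **Purpose Statement** says the study is to "provide data to support a larger study that will examine efficacy".

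**The concern.** The plan has a threshold for safety and a confidence interval, but no statement of how one bears on the other. Taken literally, any observed percentage below 10 counts as evidence of safety, however wide its interval. With 50 infants the interval is wide, so a result the sponsor could call safe may also be compatible with nearly one infant in five being affected. Whether such a result supports Hypothesis 1 would be settled only after the data are seen.

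The answer to Research Question 1 is at stake, and so is what is carried into the larger study. The protection of individual infants is not: the holding rules and the monitoring committee's review do not use the 10%.

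**Working it through.** **Inputs.** N = 50, 7 days per infant and 350 days in total; rates of 5 (assumed ceiling), 3.5 and 1.0 events per 1000 days (Sample Size Justification). Threshold 10% (Hypothesis 1). Confidence level 95% (Data Analysis), taken here as two-sided. True proportions of 10% and 15% are illustrative assumptions.

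**1. The plan's own figures.** The sample-size paragraph gives the chance of at least one affected infant as roughly 83% at 3.5 and 40% at 1.0 per 1000 days. With 350 days:

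- 1 − exp(−0.0035 × 350) = 1 − exp(−1.225) = 70.6%
- 1 − exp(−0.001 × 350) = 1 − exp(−0.35) = 29.5%

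The printed figures are not reproduced. They fit about 500 days: 1 − exp(−1.75) = 82.6% and 1 − exp(−0.5) = 39.3%. This is a separate discrepancy. It matters here only for step 5, where both totals are shown.

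**2. Which results meet the criterion as a point estimate.** On the proportion reading, x/50 < 10% means x ≤ 4. Two-sided Clopper-Pearson 95% intervals:

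| Affected infants | Estimate | Exact 95% CI |
|---|---|---|
| 0/50 | 0% | 0 to 7.1% |
| 1/50 | 2% | 0.05% to 10.6% |
| 2/50 | 4% | 0.5% to 13.7% |
| 3/50 | 6% | 1.3% to 16.5% |
| 4/50 | 8% | 2.2% to 19.2% |

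All five meet the criterion; only 0/50 has an interval that excludes 10%. Check at zero: the upper limit is 1 − 0.025^(1/50) = 7.1%.

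**3. Chance of meeting it when the true proportion is at or above the threshold.** With X ~ Binomial(50, p):

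- p = 10%: P(X ≤ 4) = 0.431
- p = 15%: P(X ≤ 4) = 0.112

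**4. Chance of meeting it under the plan's assumptions.** At a constant rate over 7 days, p = 1 − exp(−7 × rate):

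| Rate per 1000 days | p | P(X ≤ 4) |
|---|---|---|
| 5 | 3.4% | 0.97 |
| 3.5 | 2.4% | 0.99 |
| 1.0 | 0.7% | above 0.999 |

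**5. Chance that the interval excludes 10% (0/50 needed).** P(X = 0) = exp(−rate × total days):

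| Rate per 1000 days | 350 days | 500 days |
|---|---|---|
| 5 | exp(−1.75) = 17% | exp(−2.5) = 8% |
| 3.5 | exp(−1.225) = 29% | exp(−1.75) = 17% |
| 1.0 | exp(−0.35) = 70% | exp(−0.5) = 61% |

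At a true 10% of infants the chance of 0/50 is 0.9^50 = 0.5%.

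**The case against.** The strongest reply is that this is a single-arm estimation pilot with a descriptive analysis. For almost any threshold and finite sample, an estimate can fall below the threshold while its interval includes it. The interval will be reported, so a reader of 4/50 will see 2.2% to 19.2%. Under the plan's own rates the true proportion is well below 10% and the literal criterion would rarely mislead. Requiring an upper limit below 10% would add a confirmatory hurdle to a study not sized for one.

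Much of this stands. No formal test or power calculation is needed, and the concern depends on the true proportion being higher than assumed. That is possible: the primary measure counts any adverse event, the patients are in intensive care, Table 1 manages redness and laboratory findings as well as serious reactions, and the assumed rate rests on a cited study that recorded no events. The reply does not remove the difficulty that the sponsor has written a criterion for safety, and reporting an interval does not say whether 4/50 meets it.

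A reader might also infer that the two primary measures give two equally credible meanings of the 10%, each with the same flaw. The documents do not support that. Only the proportion is naturally a percentage; the other measure is stated per 100 or per 1000 days. Ten per 100 patient-days is 100 per 1000, which is 20 times the assumed ceiling. At that ceiling 0.005 × 350 = 1.75 events are expected, whereas an estimate below 10 whose interval includes 10 would need 24 to 34 events. What remains is that the word rate, together with a primary goal expressed in patient-days, leaves the intended measure unstated.

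**Conclusion.** The point holds as a gap between a stated criterion and the planned inference, and should be fixed. If the point estimate decides, 1 to 4 affected infants would count as evidence of safety although the exact upper limits run from 10.6% to 19.2%.

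These figures assume the proportion reading, all 50 infants evaluable, independent infants, and a two-sided exact interval. Steps 4 and 5 also assume a constant rate; longer follow-up raises each infant's chance of an event. Another interval method would move the boundary: a one-sided 95% exact limit for 1/50 is 9.1%, which excludes 10%. That is a reason to name the method in advance.

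A reader might infer that the study is likely to declare the baths safe wrongly, or that the design is invalid without a powered test. Neither follows. The 43% and 11% are conditional on true proportions well above what the plan assumes, and an estimation pilot may properly end with an inconclusive interval, provided that it says so.

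**What to change.** In Hypothesis 1, state that:

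- the 10% refers to the proportion of infants with at least one adverse event;
- it is a benchmark read with the two-sided exact (Clopper-Pearson) 95% interval;
- an estimate below 10% with an upper limit of 10% or more is reported as compatible with, but not evidence of, a rate below 10%;
- only an upper limit below 10% is described as evidence that the rate is below 10%.

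In the sample-size paragraph, add that with N=50 only 0/50 (upper limit 7.1%) excludes 10%, since 1/50 gives 10.6%.

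The cost is a few sentences and no new data. The estimates, intervals, holding rules and committee review do not change. The downside is that Hypothesis 1 will often not be declared supported even if the baths are as safe as assumed: step 5 gives a 17% to 70% chance over 350 days, and less with longer follow-up or if laboratory findings count as adverse events. The sample-size paragraph should say this.

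### Hypothesis 2 asserts that blood levels do not rise, but its analysis has no confidence interval and so cannot show how large a rise remains possible

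*Combined protocol and SAP*

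**What the plan says.** Hypothesis 2, under the Purpose Statement, is a negative claim: "Twice weekly CHG baths do not lead to rising (cumulative) CHG blood levels, LFTs (AST/ALT", extended to serum creatinine. It gives no size of rise. Hypothesis 1, just above it, does carry a figure: safety "as evidenced by an adverse event rate less than 10" percent.

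Data Analysis 2 is the only analysis assigned to the question. It has two parts: "Descriptive statistics including mean, median, range and frequencies will be used to describe CHG, LFTs and serum Creatinine blood levels over time", and "We will examine scatterplots and other graphical analysis of blood level dispersion over time to look for relationships". It names no slope, ratio, model or interval.

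Intervals appear once, in the opening paragraph of Data Analysis: "Our inferential statistics will calculate 95% confidence intervals around these estimates". The estimates meant are those in the sentence before: "Our primary outcome measures will be proportion of subjects that experience any adverse event, and the rate of adverse events per 100 patient-days". Blood levels are not among them.

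The Sample Size Justification rests on the adverse-event rate alone. Table 1 has cut-offs for AST, ALT and creatinine (for example "Serum Creatinine 0.7 mg/dl or greater"), each leading to discontinuation of baths in that infant. It has none for CHG, and the Purpose Statement says that "safe CHG bloodstream levels are not known".

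**The concern.** To conclude that something does not rise, a reader needs to know which rises the data rule out. A mean, a range and a scatterplot do not say. With few or noisy samples a flat-looking plot is compatible both with no change and with a sizeable rise, and the planned output does not separate the two.

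The Purpose Statement says that this pilot will supply data for a larger efficacy study, and absorption through the skin is the reason CHG is controversial at this age. If a statement about accumulation is carried forward, it should go with the size of rise that was not excluded.

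**Working it through.** **1. Figure in the plan.** There is none to reproduce for Hypothesis 2. The probabilities in the Sample Size Justification concern adverse events and have no bearing here.

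**2. Could something else in the plan supply the bound?**
- The 95% intervals: no. They refer to the adverse-event proportion and rate.
- Table 1: no. Its limits apply to single values in one infant. A creatinine that doubles from 0.3 to 0.6 mg/dl crosses none of them, and CHG has no limit.
- The data and safety monitoring committee: it receives CHG, AST/ALT, creatinine and HCT after 10 subjects, after 25 and at the end. This is real scrutiny, but it yields no estimate of change with an interval.

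**3. Inputs for an illustration.** From the documents: 50 infants (Study Sample); a baseline CHG level and then weekly Friday levels (Procedures for Obtaining CHG, ALT, AST and HCT levels); average stays of 12.7 days in the NICU and 9 to 15 days for CICU infants under 2 months (Setting). With weekly sampling, many infants would have only one or two levels after baseline. Not in the documents, so assumed: 10, 20, 30 or 50 infants with a usable pair of levels, and an SD of the within-infant log ratio of 0.5, 0.8 or 1.2.

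**4. Formulas.**
- Chance that a two-sided 5% paired t-test misses a true ratio R: P(|T| ≤ t(0.975, n−1)), where T is noncentral t with n−1 degrees of freedom and noncentrality ln(R)·√n / SD. Example, R = 1.5, n = 10, SD = 0.8: 0.4055 × 3.162 / 0.8 = 1.603; critical value 2.262; chance of missing it 0.70.
- One-sided 95% upper bound when the observed mean change is zero: exp(t(0.95, n−1) × SD / √n). Example, n = 10, SD = 0.8: exp(1.833 × 0.8 / 3.162) = 1.59.

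**5. Results** (SD 0.5 / 0.8 / 1.2).

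| Paired infants | True 50% rise missed | Upper bound on the ratio, no change |
|---|---|---|
| 10 | 37% / 70% / 84% | 1.34 / 1.59 / 2.00 |
| 20 | 7% / 42% / 70% | 1.21 / 1.36 / 1.59 |
| 30 | 1% / 23% / 57% | 1.17 / 1.28 / 1.45 |
| 50 | 0% / 6% / 35% | 1.13 / 1.21 / 1.33 |

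(The middle entry for 30 infants is 0.235 before rounding.) With R = 2 in the same formula, a true doubling is missed 3% / 32% / 63% of the time with 10 infants, 0% / 4% / 31% with 20 and 0% / 0% / 2% with 50. The upper limit of a two-sided 95% interval uses t(0.975, n−1) and is higher: 1.43 / 1.77 / 2.36 with 10 infants and 1.15 / 1.26 / 1.41 with 50.

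The plan contains no such test. The table shows how much a formal look could miss; reading a plot by eye has no stated error rate.

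**The case against.** The strongest reply is that this is a single-arm pilot aimed at the adverse-event rate. The CHG assay is for research use only and has no certified calibrators, and CHG levels are not the primary means of judging reactions. Description is a reasonable ambition in that setting. This stands, and it lowers the weight of the point. What it does not rescue is the wording of Hypothesis 2, which is an assertion and not a description.

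A reader might infer that the investigators will take a flat plot as proof of no accumulation. The documents do not say so: Data Analysis 2 looks for relationships and states no rule for accepting the hypothesis.

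A reader might also infer that the plan must fix a largest tolerable rise in advance. The documents offer no basis for one in CHG, since they say that safe levels are unknown. Any margin would be debatable, and an interval is informative without it.

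Finally, a reader might take the 10-infant row as what to expect. It is one end of the range. If all 50 infants give a pair and the SD is 0.5, a 50% rise would almost never be missed. The number of pairs and the SDs are assumptions.

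**Conclusion.** The concern holds in limited form. Hypothesis 2 claims that levels do not rise; the planned output has no interval for any blood level; so it cannot show what rise remains compatible with the data and cannot support the claim as worded. That conclusion rests on the text alone.

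The size is conditional. Across the assumed SDs and 10 to 50 pairs, the chance of missing a true 50% rise runs from about 0% to 84%. With no true rise, the one-sided upper bound is about 1.3 to 2.0-fold with 10 infants and 1.1 to 1.3-fold with 50. The documents do not show where in that range the trial would fall.

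Severity is minor: this is not the primary quantitative goal of the pilot.

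**What to change.** - **Hypothesis 2.** Reword it as an aim: to estimate the within-infant change in CHG, AST, ALT and creatinine during twice-weekly baths.
- **Data Analysis 2.** For each analyte, report the within-infant change from baseline with its 95% confidence interval, either as a geometric mean ratio or from a repeated-measures model on the log scale with infant as a random effect and time since first bath. The model is preferable, because follow-up may last from days to 12 weeks and a single ratio would pool unlike intervals.
- **Which samples.** Use all of them, including the value that triggers stopping of baths. Otherwise infants whose values rose most would lose their highest reading, and the remaining levels would look falsely stable.
- **CHG below the quantification limit.** Use a censored-data method, so that the same ratio and interval can be reported.
- **Wording of results.** State any conclusion of no accumulation only together with the upper limit; otherwise report that accumulation was neither shown nor excluded. With no control arm, describe change during bathing, not change caused by it.
- **Check the baseline.** Human Subjects lists AST, ALT and creatinine at baseline. The blood-volume reckoning under Assessment for Iatrogenic Anemia allows 0.5 mL at baseline, which is the volume of the CHG sample alone. Confirm that baseline values for the other three will be available, from routine care or otherwise.

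The cost is a few sentences and a small calculation on levels the plan already intends to collect. Provided the baseline values are available, it needs no extra blood, staff or infants. The downside is that the reported result may be inconclusive.
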